6.0 CLINICAL STUDY DESIGN

6.1 Clinical study design

<Clinical study design>

This is a multi-center, randomized, open-label, parallel-group comparison study to assess the reduction in treatment burden during the administration of a DPP-4 inhibitor (trelagliptin or a daily DPP-4 inhibitor) for 12 weeks in patients with type 2 diabetes on diet and exercise therapy only.

Eligible study subjects as a result of eligibility assessment after giving informed consent will be randomized to either of the study drug (trelagliptin) group or the comparative drug (daily DPP-4 inhibitor) group as specified in Section 8.4.

< Dosage and Administration>

The study drug group: Trelagliptin 100 mg is orally administered once weekly. Trelagliptin 50 mg is orally administered once weekly in patients with moderate renal impairment.

The comparative drug group: An inhibitor is orally administered at the dosage and administration in the package inserts for each drug.

<Evaluation period and visit frequency for study subjects>

Evaluation period: 16 weeks (Screening period: 4 weeks; treatment period: 12 weeks)

Number of visits: total 4 visits

A study subject will visit to his/her study site at the start of the screening period (Visit 1; Week -4), at the start of the treatment period (Visit 2; Week 0 of the treatment period), during the treatment period (Visit 3; Week 4 of the treatment period) and at the end of the treatment period (Visit 4; Week 12 of the treatment period).

<Planned number of study subjects>

As the number of randomized subjects:

The study drug (Trelagliptin) group 120 subjects

[figure not shown]
The comparative drug (daily DPP-4 inhibitor) group 120 subjects

<Number of study sites>

Approximately 15

Figure 6 (a) shows an outline of the clinical study design. Refer to Appendix A for schedule of examinations, observations, and evaluations.

CONFIDENTIAL

CONFIDENTIAL

Figure 6.a Outline of the clinical study design

<Outline of the clinical study>

Duration of treatment: 12 weeks

Number of visits: 4 visits

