9.2.4 Treatment period (Week 12) or discontinuation

Tests, observations and evaluations performed at the end of study treatment (Visit 4: Week 12) are shown below.

- Physical examination
- body weight
- Concomitant drugs
- Laboratory tests (blood chemistry and urinalysis)
- Treatment Compliance
- DTR-QOL Questionnaire
- DTSQ
- The Basic Information on Study Subjects (Your Basic Profile)
- Adverse event
- Hospitalization for type 2 diabetes

Tests, observations and evaluations performed at the discontinuation are shown below.

- Physical examination
- Concomitant drugs
- Laboratory tests (blood chemistry and urinalysis)
- Treatment Compliance
- DTR-QOL Questionnaire
- DTSQ
- The Basic Information on Study Subject (Your Basic Profile)
- Adverse event evaluation
- Hospitalization for type 2 diabetes
- The reason for the discontinuation

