2 EFFICACY EVALUATIONS	11
2.1 Primary Endpoint and the Analytical Methods	11
2.2 Secondary Endpoints and the Analytical Methods	11
2.3 Other Analysis	12
2.4 CONSIDERATIONS on STATISTICAL ANALYSIS	15
2.4.1 Adjustments for Covariates	15
2.4.2 Handling of Dropouts or Missing Data	15
2.4.3 Interim Analysis and Early Discontinuation	15
2.4.4 Multicenter Studies	15
2.4.5 Multiple Comparisons/Multiplicity	15
2.4.6 Use of an Efficacy Subset of Subjects	15
2.4.7 Active-Control Studies Intended to Show Equivalence	15
2.4.8 Subgroup Analysis	15
3 SAFETY EVALUATION	16
3.1 Treatment -Emergent Adverse Event	16
3.1.1 Brief Summary of Adverse Events	16
3.1.2 Display of TEAE	17
3.2 Frequency of Hypoglycemia	18

3.3 Hospitalization related to type 2 diabetes mellitus	18
4 LISTINGS.....	18
Significance level, Confidence coefficient	21
REVISION HISTORY.....	22

DEFINITIONS of TERMS

- Treatment -emergent adverse event (TEAE) : The AE which occurs after taking the first dose of trial medication.
- Summary Statistics: Number of subjects, mean, SDs, maximum values, minimum values, and quartiles
- BMI: Body Mass Index
- MedDRA: Medical Dictionary for Regulatory Activities
- QOL: Quality Of Life
- WHO: World Health Organization
- DTSQ: Diabetes Treatment Satisfaction Questionnaire
- DTR -QOL: Diabetes Therapy -Related QOL
- Subject with hypoglycemia: The subject with AE related to hypoglycemia
- Non Serious TEAE: Non -Serious TEAE is defined as Non -Serious TEAEs of at least 5% in any treatment group by SOC and PT. (if no event exceeds the 5% frequency, cutoff is lowered to 2%).

ANALYSIS SET

- Full Analysis Set
The subjects who were randomized and received at least one dose of the Trelagliptin or Daily DPP-4 inhibitor
- Safety Analysis Set
The subjects who received at least one dose of the Trelagliptin or Daily DPP-4 inhibitor

TIME WINDOW

For each assessment, observation and evaluation item, evaluable data is selected according to the following table. When there are multiple data exist within a time window, the one with the closest date to the reference date is adopted, and if the differences from the reference date are the same for multiple data, the later one is adopted.

1) DTR -QOL Questionnaire, The Basic Information on Study Subject, Laboratory Test (HbA1c)

Analysis Visit	Reference Date	Time Allowance (Number of Study Days)
Week -4	-30	-30～-15
Week 0	-1	-14～-1
Week 4	28	21～35
Week 12	84	70～97

Analysis Visit	Reference Date	Time Allowance (Number of Study Days)

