End of Study	The latest date in treatment period	21～97

2) DTSQ, Laboratory Test (except HbA1c)

Analysis Visit	Reference Day	Time Allowance (Number of Study Days)
Week -4	-30	-30～-2
Week 0	-1	-1
Week 4	28	21～35
Week 12	84	70～97
End of Study	The latest date in treatment period	21～97

OTHER DATA HANDLING

Items	Method	Conditions
DTR -QOL Questionnaire Factor1: Burden on Social Activities and Daily Activities	The sum total of questions number 1 -13 was converted into a 0 -100 score [the best (91) = 100 and worst (13) = 0].	For a factor with <50% missing data, the mean value (round off 2 digits) calculated from available answers is applied to cover the missing data.
DTR -QOL Questionnaire Factor 2: Anxiety and Dissatisfaction with Treatment	The sum total of questions number 14 and 19 -25 is converted into a 0 -100 score [the best (56) = 100 and worst (8) = 0].	For a factor with <50% missing data, the mean value (round off 2 digits) calculated from available answers is applied to cover the missing data.
DTR -QOL Questionnaire Factor 3: Hypoglycemia	The sum total of questions number 15 -18, and is converted into a 0 -100 score [the best (28) = 100 and worst (4) = 0].	For a factor with <50% missing data, the mean value (round off 2 digits) calculated from available answers is applied to cover the missing data.
DTR -QOL Questionnaire Factor 4: Treatment Satisfaction	Each score of question number 26 -29 is reversed (i.e., 1 converted to 7, 7 converted to 1, and so on; the converted scores, where 7 is the best	For a factor with <50% missing data, the mean value calculated from available answers is applied to cover the missing data.

Items	Method	Conditions
	and 1 is the worst, had the opposite sequence of the original scores). The converted scores are then added up, and the total is converted into a 0 -100 score [the best (28) = 100 and worst (4) = 0].	
DTR -QOL Questionnaire Total Score of all Questions	1) Each score of question number 26 -29 was reversed.((i.e., 1 converted to 7, 7 converted to 1, and so on;). Factor1 – Factor 4 are calculated as described above.(Not converted) 2) Factor 1 - Factor 4, which calculated by the method described above, are subsequently added up, and converted into a 0 -100 score [the best (203) = 100 and worst (29) = 0].	The total score of whole questions is not calculated if a total score of any of the four factors was unavailable.
DTSQ Total Score	Item 1, 4, 5, 6, 7, 8 scores are added up,	All data must not be missing.

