Planned Number of Dosage of Trelagliptin (tablets)	(The last administration date - the first administration date) / 7) +1. * Cut off to the whole number	All data must not be missing.
Planned Number of Dosage of Daily DPP -4 Inhibitor (tablets)	(The last administration date - the first administration date) \times number of daily dose \times number of tablets at the first administration date	All data must not be missing.
Study Medication Compliance (%)	Actual number of dosage / Planned number of dosage \times 100 (tablets)	All data must not be missing.
Days after Administration (Days)	Examination/observation/evaluation date - the first administration date +1	All data must not be missing.

Items	Method	Conditions
Duration of Diabetes (year)	$\{ (\text{The first administration date (year)} \times 12 + \text{The first administration date (month)}) - (\text{Onset Date of Diabetes (year)} \times 12 + \text{Onset Date of Diabetes (month)}) \} / 12$ (rounded off two decimal places)	All data must not be missing. If only the month of the onset of diabetes is unknown, the month of the onset of diabetes is regarded as "January".
8-OHdG/Creatinine (ng/mg CRE)	8-OHdG (ng/mL) / Urine creatinine (mg/dL) $\times 100$	All data must not be missing.

Display digit

Item	Defitintion
Mean, Confidence interval, Quartiles	Round statistics down to the 1 digits lower than significant digits of the data.
Standard Deviation	Round to the 2 digits lower than significant digits of the data.
Minimum and Maximum Values	Display the data at the significant digits.
Proportion, Percentage	Round to the one decimal place.
P-value	Round down to four decimal places. If p-value is less than 0.0001, display "p<0.0001"

AE related to Hypoglycaemia

AE related to Hypoglycaemia is defined as below.

PT Code	PT Name (Japanese)	PT Name (English)
10020993	低血糖	Hypoglycaemia
10040576	低血糖ショック	Shock hypoglycaemic
10065981	低血糖性意識消失	Hypoglycaemic unconsciousness
10048803	低血糖性痙攣	Hypoglycaemic seizure
10021002	低血糖性脳症	Hypoglycaemic encephalopathy
10021000	低血糖昏睡	Hypoglycaemic coma
10020997	無自覚性低血糖	Hypoglycaemia unawareness
10054998	神経低糖症	Neuroglycopenia

1 SUBJECTS, DEMOGRAPHIC and OTHER BASELINE CHARACTERISTICS

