2 EFFICACY EVALUATIONS

2.1 Primary Endpoint and the Analytical Methods

Analysis Set: Full Analysis Set

Items: Change from Baseline in DTR-QOL Total Score at End of Study (Week 12)

Method: Analysis of covariance (ANCOVA) is conducted to compare between the treatment groups using "Change from baseline in DTR-QOL total score by the end of treatment [the End of Study (Week 12) - baseline (Week 0)]" as a dependent variable; DTR-QOL Total Score at the start of the screening period(<80 or ≥ 80) and HbA1c ($<8.0\%$ or $\geq 8.0\%$) at the start of the screening period as covariates; and "treatment group" as an independent variable. The level of significance is defined as 5% (two-sided).

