2.4.2 Handling of Dropouts or Missing Data

Data which are not adopted as a result of data missing of each analysis item or data handling in accordance with this statistical analysis plan item will be excluded from the analysis target for the statistical test or estimation of the evaluation.

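### A final visit after Day 97 fits no SAP window, so that subject's primary value becomes the Week 4 score or is lost

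*SAP*

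**What the plan says.** The Time Window section of the SAP has two tables. Table 1 covers DTR-QOL, the Basic Information questionnaire and HbA1c; table 2 covers DTSQ and the other laboratory tests. The on-treatment rows are the same in both:

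| Analysis visit | Reference | Days admitted |
|---|---|---|
| Week 4 | Day 28 | 21 to 35 |
| Week 12 | Day 84 | 70 to 97 |
| End of Study | "The latest date in treatment period" | 21 to 97 |

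The selection rule is: "When there are multiple data exist within a time window, the one with the closest date to the reference date is adopted". Study day is defined as "Examination/observation/evaluation date - the first administration date +1", so the first dose is on Day 1.

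SAP 2.1 gives the primary item as "Change from Baseline in DTR-QOL Total Score at End of Study (Week 12", closing the bracket after the week number. SAP 2.2 lists Week 12 and End of Study as separate analysis visits. Under SAP 2.4.2, data that are missing or not adopted under the handling rules "will be excluded from the analysis target for the statistical test or estimation of the evaluation".

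Protocol 6.1 states "Number of visits: total 4 visits". By Protocol 9.2.3 and 9.2.4, a completer answers the DTR-QOL on treatment only at Week 4 and Week 12. Protocol 9.2.4 introduces the final visit with "Tests, observations and evaluations performed at the end of study treatment (Visit 4: Week 12) are shown below" and gives no tolerance in days. The protocol refers to Appendix A for the schedule; that appendix is not in the text available for this review.

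**The concern.** The days admitted decide which records may compete; the reference date only ranks those that are let in. A final questionnaire completed on Day 98 or later is let in nowhere. The primary endpoint is the change at the end of treatment, yet for such a subject it would be taken about a third of the way through treatment, or not at all, although a final score was collected.

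The same row governs the End of Study values for DTSQ, HbA1c and the other laboratory tests. A substitution would also be hard to spot. The DTR-QOL listing in SAP 4 shows the analysis visit but no assessment date, whereas the laboratory listing shows a sample date. The deviation categories in SAP 1.1.4 have no visit-timing class other than the catch-all.

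**Working it through.** **1. The rule applied to example visit days.**

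| Assessment days | Week 12 value | End of Study value |
|---|---|---|
| 28 and 84 | Day 84 | Day 84 |
| 28 and 97 | Day 97 | Day 97 |
| 28 and 98 | none | Day 28 |
| 36 and 98 | none | Day 36 |
| 20 and 98 | none | none |

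For the subject seen on Days 28 and 98, the value labelled End of Study is 98 − 28 = 70 days older than the actual final score. The row accepts a score up to 84 − 21 = 63 days before Day 84 but rejects one 98 − 84 = 14 days after it.

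**2. The planned figures.** Protocol 13.3 assumes mean changes of 19.0 and 14.4 (difference 4.6), SD 12.1, two-sided 5% and 80% power. Then n = 2 × (1.960 + 0.842)² × 12.1² / 4.6² = 109 per group by the normal approximation, and 109.6, so 110, for a t-test. Power at 110 is 0.805 (normal) or 0.801 (t-test). Allowing for 8% dropout, 110 / 0.92 = 119.6, so 120. The plan's 110 and 120 reproduce.

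**3. Effect if the Week 4 score is substituted.** The documents give neither a lateness rate nor a Week 4 gain, so both are assumptions. Let f be the share of completers seen after Day 97 (1% to 5%), and r the Week 4 gain as a fraction of the Week 12 gain (0.3 to 0.8). The arm mean becomes gain × (1 − f × (1 − r)).

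| Late, trelagliptin / daily | r = 0.3 | r = 0.8 | Shift from 4.6 |
|---|---|---|---|
| 5% / 5% | 4.6 × 0.965 = 4.44 | 4.6 × 0.990 = 4.55 | −0.16 to −0.05 |
| 5% / 1% | 18.335 − 14.299 = 4.04 | 18.810 − 14.371 = 4.44 | −0.56 to −0.16 |
| 1% / 5% | 18.867 − 13.896 = 4.97 | 18.962 − 14.256 = 4.71 | +0.11 to +0.37 |

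For scale, the planned standard error of the difference is 12.1 × √(2/110) = 1.63. A shift of 0.16 is about 0.1 standard error, and 0.56 is about a third.

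**4. Effect if late completers are dropped instead.** With 110 × (1 − f) per group, power falls from 0.805 to 0.801 at 1% late, 0.797 at 2% and 0.785 at 5% (normal approximation).

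**The case against.** Four points on the other side carry weight.

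- **The row can be read coherently.** It may mean the last value within Days 21 to 97, a deliberate cap 13 days after Day 84. A reader might infer that the SAP contradicts itself because the reference date falls outside its own window. That needs the treatment period to run past Day 97, which the documents do not establish; the protocol sets treatment at 12 weeks. This is a gap in the rule, not a strict contradiction. The cap still serves neither possible aim. If closeness to Week 12 mattered, a Day 28 score could not stand in for a Day 98 score. If the last on-treatment value mattered, the cap defeats it. Reading the period as strictly 12 weeks would also bar Days 86 to 97, which the SAP accepts.
- **Appendix A is unseen.** A reader might infer that a Day 98 visit is within protocol because the supplied text gives no tolerance. That cannot be concluded; a tolerance may stand in the appendix. It would not change what the SAP does with a late record.
- **A late score is not necessarily on treatment.** The protocol lists prescriptions at Weeks 0 and 4 only, without quantities, and its ban on other diabetes drugs ends at Week 12. An End of Study window with no upper limit and no condition could admit scores taken off drug or on other therapy. This stands, and it limits the fix.
- **A Week 12 estimate is already planned.** SAP 2.2 gives adjusted differences for the total score at Week 12 (Days 70 to 97), free of Week 4 substitution. That would help reveal a distortion, but it would not recover the late scores and is not described as a rerun of the primary ANCOVA.

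**Conclusion.** The rule gives the wrong primary value for a subject whose Visit 4 falls after Day 97 if End of Study is the primary visit, and no value if Week 12 is. The SAP does not settle which of the two applies. This follows from the SAP text alone.

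The size is unknown and probably small. With equal lateness of 5% the assumed difference shrinks by about 0.05 to 0.16 points, and by less at lower rates. A reader might infer from the −0.56 figure that the effect could be biased by about 12% (0.56 / 4.6). That is the worst corner of assumed inputs, with five times as much lateness on trelagliptin and r = 0.3. The documents give no reason to expect lateness to differ by arm, and the sign reverses if the daily arm is later. The point justifies correcting the rule because the correction is cheap; it is not evidence of a biased result.

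**What to change.** In the End of Study row of both window tables, add:

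- Where Visit 4 was attended while the subject was still on the allocated drug and no prohibited diabetes drug had been started, the Visit 4 value is the End of Study value, even if it falls after Day 97.
- A Week 4 value is never carried to End of Study for a subject who attended Visit 4.

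In SAP 2.1, state that the primary analysis uses this End of Study value. Keep Days 70 to 97 for the Week 12 by-visit summaries, and run the primary ANCOVA restricted to Days 70 to 97 as a sensitivity analysis.

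The cost is one row in two tables, one sentence in SAP 2.1 and one extra model run. The on-drug condition can be checked against the dose dates and concomitant-medication dates already planned for listing in SAP 4. There are two downsides. A few scores measured more than 13 days after Day 84 enter the primary analysis. A late attender who fails the on-drug condition has no End of Study value and is excluded under SAP 2.4.2; the number of such subjects should be reported by arm.

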7.4 Study subject management

The principal investigator and investigator shall instruct the research subject the items below.

- (1) Give instructions to take allocated oral hypoglycemic drug as directed.
- (2) If hypoglycemia symptom (hunger abnormal, feeling of weakness, trembling of hands and fingers, cold sweat, palpitations, etc.) is observed, take glucose or sucrose (sugar), and if it does not improve give instructions to visit promptly.
- (3) On visit days for planned laboratory tests, give instructions not to take oral hypoglycemic drug scheduled to be taken on that day. Further, at each visit, have the research subject report if drug has been taken or not the day before, and on the day of visit.
- (4) On visit days for planned laboratory tests, give instructions for fasting \geq 10 hours before visit (excluding start of observation period).
- (5) For research subjects of childbearing potential, give instructions to use adequate contraception. If pregnancy is discovered, have the research subject report promptly, and discontinue the research immediately.
- (6) The principal investigator and investigator shall instruct the research subject to adhere to instructed prohibited concomitant drugs. When drugs are taken other than the drugs prescribed by the principal investigator and investigator, have the research subject report its content.
- (7) Regarding subjective symptoms/objective findings, have the research subject report at visit the necessary items from its contents, onset date, degree, outcome and date of outcome.

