7.6 Procedures for discontinuation of individual study subjects

The principal investigator or investigator shall terminate a study subject's study participation when the study subject meets the criteria described in Section 7.5. Individual study subjects may discontinue their study participation without giving a reason at any time during the study. Should a

study subject's participation be discontinued, the primary reason for termination shall be recorded on the CRF by the principal investigator or investigator. In addition, efforts shall be made to perform all tests/observations/evaluations scheduled at the time of discontinuation.

CONFIDENTIAL

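### SAP compliance formulas: the daily planned count leaves out one dosing day, and weekly truncation loses a dose when the last one is early, so full adherence can read above 100%

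*SAP*

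**What the plan says.** All the rules are in the SAP's Other Data Handling table.

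- **Weekly arm.** Planned doses are "The last administration date - the first administration date) / 7) +1", with the footnote "Cut off to the whole number". The printed brackets do not balance, but truncating before or after adding 1 gives the same answer.
- **Daily arm.** Planned tablets are (last minus first administration date) × doses per day × "number of tablets at the first administration date". There is no +1.
- **Compliance.** "Actual number of dosage / Planned number of dosage", times 100. No cap is stated.
- **Days after Administration**, in the same table, is counted inclusively: "Examination/observation/evaluation date - the first administration date +1".

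The table does not define the last administration date or the actual number of doses. SAP 2.3 gives summary statistics of compliance by treatment group and no test. For days with planned laboratory tests, Protocol 7.4(3) tells investigators to "give instructions not to take oral hypoglycemic drug scheduled to be taken on that day".

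**The concern.** Subtracting two dates counts the intervals between them, not the dosing days. The weekly row and the study-day row allow for this and the daily row does not, so the two arms are counted by different rules. Truncation can also remove a dose from the weekly denominator. Fully adherent subjects can then score above 100%, by an amount that depends on arm and timing.

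Compliance is a named other endpoint, and Protocol 4.1 gives better adherence as an expected benefit of weekly dosing. Readers are likely to compare the two columns, although the SAP plans no formal comparison. At stake is the credibility of that descriptive table.

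**Working it through.** The documents state no compliance figure to reproduce, so the formulas are applied to assumed dosing histories.

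**Inputs.** First dose on Day 1; 12 weeks of treatment (Protocol 6.1); visits on the SAP reference days 28 and 84; one tablet per dose; last administration date read as the last dose taken.

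**Daily, as written:** planned = last − first.

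| Once-daily history | Actual | Planned | Compliance |
|---|---|---|---|
| One dosing day | 1 | 1 − 1 = 0 | undefined |
| All doses, last on Day 7 | 7 | 6 | 116.7% |
| All doses, last on Day 14 | 14 | 13 | 107.7% |
| All doses, last on Day 27 | 27 | 26 | 103.8% |
| Completer, Days 28 and 84 withheld | 82 | 83 − 1 = 82 | 100% |
| Day 28 taken, Day 84 withheld | 83 | 82 | 101.2% |
| Days 28 and 84 both taken | 84 | 83 | 101.2% |

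Twice-daily dosing doubles both counts: 168/166 = 101.2% when every dose over 84 days is taken. The completer reaches 100% because the dose withheld on Day 28 cancels the missing +1. The SAP does not give this as a reason for the formula. The subject with one daily dosing day has no value and drops out under SAP 2.4.2, while one weekly dose scores 1/1.

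**Weekly, as written:** planned = floor((last − first)/7 + 1).

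- Twelve doses, last on Day 78: floor(77/7 + 1) = 12, so 12/12.
- Last dose one day early, Day 77: floor(76/7 + 1) = floor(11.857) = 11, so 12/11 = 109.1%. The same holds up to seven days early.
- Last dose one to six days late (Days 79 to 84): planned stays 12, so 12/12.
- If dosing continues and the dose due on Day 85 is taken on Day 84: floor(83/7 + 1) = 12, so 13/12 = 108.3%.

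**Doses missed at the end, subject still in the study and on drug.** Suppose the last two weeks before a Day 84 visit are missed.

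- Weekly, last dose Day 64: floor(63/7 + 1) = 10, so 10/10 = 100%. Against the 12 doses scheduled on Days 1, 8, …, 78 it is 10/12 = 83.3%.
- Daily, last dose Day 69 with Day 28 withheld: 68/(69 − 1) = 68/68 = 100%. Against Days 1 to 83 less Day 28 it is 68/82 = 82.9%.

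**The case against.** **The ordinary daily subject is scored correctly.** This stands for anyone who follows 7.4(3) and stays past Week 4. For example, a last dose on Day 50 with Day 28 withheld gives 49/49. A bare +1 would make the adherent completer worse, at 82/83 = 98.8%. A reader might infer that the whole daily arm is inflated; the documents do not support that.

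**Few subjects are affected.** Protocol 13.3 assumes 8% discontinuation and cites an annual rate. On that annual basis, 120 × 0.08 × 4/52 = 0.7 daily-arm subjects would leave in the first four weeks. If the 8% left evenly over 12 weeks, it would be 120 × 0.08 × 4/12 = 3.2. Three subjects at 116.7% would raise a 120-subject mean by 3 × 16.7/120 = 0.4 points. This stands as to size. It does not cover subjects who take the Day 28 dose or weekly subjects whose last dose is early, and the documents give no frequency for either.

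**Ending the interval at the last dose is a choice.** It may be tempting to call this an arithmetic error that hides dropouts. The documents do not support that. Measuring dosing between first and last dose, separately from persistence, is a legitimate definition. Protocol 7.6 ends a subject's "study participation when the study subject meets the criteria described in Section 7.5", and no off-treatment follow-up is planned. SAP 1.1.3 reports disposition, and SAP section 4 lists dose dates and unused quantities. What remains is a limit of the definition, and only if the undefined term means the last dose taken. If a scheduled date was meant, that limit disappears.

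**Conclusion.** Wrong as written, and minor. The daily row lacks the +1 used elsewhere in its own table. The excess is D/(D-1) for adherent subjects who leave before Week 4 and 101.2% for completers who take the Week 4 visit-day dose. Weekly truncation gives 109.1% when the last of twelve doses is early, and nothing when it is on time or one to six days late. For each tenth of the weekly arm so affected, the arm mean rises by 9.1/10 = 0.9 points.

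The figures assume visits on Days 28 and 84. A reader might infer a bias towards one arm. The documents do not support that either, because both faults raise scores, one in each arm, and their frequencies are unknown. Compliance defines no analysis set and enters no model, so the primary and secondary analyses are unaffected.

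**What to change.** These are counting rules only; nothing subjects are told to take changes.

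1. **Daily planned** = ((last − first + 1) × doses per day − doses withheld as instructed on visit days between first and last dose) × tablets per dose. This gives 82/82 for the adherent completer, 27/27 for a last dose on Day 27, 83/83 if the Day 28 dose was taken and Day 84 withheld, and 1/1 for one dosing day.
2. **Weekly planned** = (last − first)/7 rounded to the nearest whole number, + 1. A last dose up to three days early or late gives 12/12, and the Day 85 dose taken on Day 84 gives 13/13. There is a price: a last dose four to six days late now reads 12/13 = 92.3%. One four or more days early still reads 12/11, for example Day 74: 73/7 = 10.4, rounded to 10, + 1 = 11.
3. **Define** the last administration date and the actual number of doses. For subjects who stop drug or leave, keep the interval ending at the last dose. Running it to discontinuation would score a daily subject taken off drug for an adverse event after Day 20 and discontinued on Day 28 at 20/27 = 74.1%.
4. **Add one supplementary summary** for subjects still in the study and not withdrawn from drug, with the interval ending the day before the Week 12 visit. The two-week gap then reads 10/12 = 83.3% weekly and 68/82 = 82.9% daily. Here the weekly count should be the scheduled dosing days (Days 1, 8, …, 78), because putting Day 83 into rule 2 gives 82/7 = 11.7, rounded to 12, + 1 = 13. It should not fall below the rule 2 count, so that an early dose before an early visit does not exceed 100%.

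The cost is SAP wording and a little programming. The data are already collected: administration times and quantities prescribed and unused (Protocol 9.1.11), tablets per administration (Protocol 8.4), and visit-day intake, since 7.4(3) has investigators "have the research subject report if drug has been taken or not the day before, and on the day of visit".
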